Vaginal CO2 Laser for Stress Incontinence: A randomized controlled trial (1)

Trial registration: [to come at clinical trialgs.gov](#)

27.01.2019

Funding: Hvidovre hospital. The funder has no role in study design, data collection, data analysis, data interpretation, or writing the report

Written by: [name], [name] and [name]

This protocol has been developed in accordance with the SPIRIT guidelines. Numbers referring to requirements from Danish Ethics Committee has been written in parenthesis.

Introduction (2)

Urinary incontinence (UI) is a common condition affecting nearly 50% of women at some point in their life (MinassianVA, *Obstet Gynecol.* 2008). The prevalence is increasing with age and is often a great burden for the patient with serious implications on the quality of life (Schreiber, ACTA 2017). Studies report that only 25% of affected women seek help for their incontinence symptoms and of those, less than half receive treatment (MinassianVA, *Int Urogynecol J.* 2012). UI is typically divided into 3 main types, namely (i.) stress urinary incontinence (SUI), which affects up to 30% of women (Ogah, Neurol. and uro., 2011) and is characterized by involuntary loss of urine with increases in intra-abdominal pressure such as exercise and coughing, (ii.) urgency incontinence, which is characterized by a sudden compelling desire to pass urine that is difficult to defer (Abrams, Neurolourol. Urodyn, 2010) and (iii.) mixed urinary incontinence, where symptoms of both stress and urgency incontinence are found. SUI is caused by poorly functioning urethral closure and is characterised by loss of anatomic support in the pelvic area. This anatomic defect can be caused by multiple pregnancies, vaginal childbirth, obesity and repetitive increase in intra-abdominal pressure, such as seen in chronic obstipation or coughing, heavy lifting and high-impact exercise (HandaVL, *Obstet Gynecol.* 2011// HandaVL, *Am J Obstet Gynecol.* 2004 //LawrenceJM, *Diabetes Care.* 2007// Nygaard IE, *Am J Obstet Gynecol.* 2016). Urgency incontinence is typically idiopathic although it is also seen in women with general neurologic disorders, such as Parkinson disease, multiple sclerosis and pelvic or spinal nerve injury.

Initial treatment of urinary incontinence typically starts with non-invasive measures, due to the fact that related benefits are associated with low risks and limited expenses. These measures include lifestyle modifications, such as weight loss, smoking cessation, treatment of obstipation, alcohol- and caffeine-restriction, avoidance of excess fluid intake and fluid- and voiding-management. Systematic reviews report that pelvic floor exercises in women with IU are beneficial (Hay-Smith EJ *Cochrane Database Syst Rev.* 2011). A systematic review found that 59% of women with stress urinary incontinence were cured after 12 months of supervised pelvic floor muscle training. (RiemsmaR,HagenS, *BMC Med.* 2017).

Treatment of SUI aims at strengthening the pelvic floor and stabilize urethral mobility. Non-invasive treatment of SUI includes pelvic floor muscle training and use of vaginal devices. There are studies that indicate that bladder control pessaries are effective and may be preferable for women, who have SUI during specific situations as for example, during exercise (Lipp A, *Cochrane Database Syst Rev* 2014.) Furthermore, there are over-the-counter vaginal devices, such as Contrelle® or Impressa® that are SUI specific, and may be better tolerated as they are easier to self- administer. Women with symptoms of SUI in spite of conservative non-invasive treatment may be candidates for surgery. Currently, the most commonly performed surgery for SUI is the midurethral sling, a 30-minute outpatient procedure in which a synthetic mesh sling is placed through either a retropubic or transobturator approach. (Nager CW. *Am J Obstet Gynecol.* 2016). The midurethral sling is the most extensively studied procedure for SUI, with documented short-term efficacy (>5 yrs.) between 43- 92% (Ford AA, *RCochrane Database Syst Rev.* 2015// Schimpf MO, *Am J Obstet Gynecol.* 2014). Complication rates of this procedure is low, but includes risk of bladder- or

urethral lesion, urinary retention, haematoma, pain, worsening of urgency, dyspareunia and sling erosion (Ford AA, *R Cochrane Database Syst Rev*. 2015// Morling JR, *Lancet*. 2017// Anger JT, *Urology*. 2014)

A novel minimal-invasive method of treating UI, has been introduced in the recent years, namely vaginal laser treatment. The use of laser has now been described in pelvic organ prolapse, UI and genito-urinary symptoms of menopause. Bhide et al have recently published a review article, where they describe 5 prospective cohort studies of laser-treatment of SUI (Table 1) (Bhide AA, *Int. Urogyn. Journ.*, 2018). Gambacciani et al. published a study of 45 women with IU, of whom 19 had SUI (Gambacciani M, *Ital J Gynaecol Obstet*. 2015). Vaginal treatment included application of YAG laser 3 times with 1 month apart and symptoms were evaluated at baseline and at a 3- and 6-month follow-up with ICIQ-U1 SF questionnaire. The treatment induced a significant decrease in ICIQ-U1 at 3 months with decrease of ICIQ scores from 12.0+/- 1.8 to 5.6+/-2.6 and this was still significant at 6 months. Ogrinc et al published a study on the use of YAG laser on women with IU, of whom 115 had SUI. Symptoms were evaluated at baseline and at 12-months follow-up with Incontinence Severity Index (ISI) and all women showed significantly decreased ISI scores (Ogrinc UB, *Lasers Surg Med*. 2015). Fistonic et al published two studies of the use of a single application of YAG laser in the treatment of SUI and evaluated with ICIQ-U1 SF. The first study evaluated 31 women with SUI and follow-up at 1- 2- and 6- months showed significantly reduced ICIQ-IU SF scores albeit many of women were lost to follow-up (Fistonić N., *YAG. Lasers Med. Sci.* 2016). The next study of 73 women with SUI showed 72.3% experiencing improvement of symptoms, 23.4% experiencing no change and 4.3% experiencing worsening (Fistonić N, *Climacteric*. 2015). Pardo et al. evaluated the vaginal erbium:YAG laser in a longitudinal prospective study in 42 patients with SUI (Pardo JI, *Eur J Obstet Gynecol Reprod Biol*. 2016). Treatment was applied twice with 21- 28 days apart and median ICIQ-IU SF scores, which was reported at 3- and 6- months follow-up, was significantly reduced; 78.6% reported improvement of SUI and 38.1% reported a complete remission of SUI. Gambacciani et al. studied 205 post-menopausal women of which 114 were diagnosed with SUI. In this study, three vaginal erbium:YAG laser applications were administered at 30-day intervals, and ICIQ-SF was used to evaluate before and after treatment with follow-up up to 24 months post treatment (Gambacciani M, *Climacteric*. 2018). The results demonstrated a significant decrease in ICIQ-SF scores from baseline to 12 months post treatment. However, at 18 and 24 months, ICIQ-SF scores were not significantly different from baseline. All 5 studies used a non-randomised selection of patients and treatment effect was estimated by using pre-treatment incontinence scores for comparison . Only the YAG laser has been evaluated in a randomized trial with 114 women which found significant improvement in the ICIQ-SF scores in the treatment arm compared with placebo (Bleganje 2018). None of the mentioned studies showed any serious complications or side effects of the laser treatment.

The FDA has recently pointed out that there is a lack of evidence of efficacy and safety of vaginal laser in the treatment of urogenital symptoms in women

(<https://www.fda.gov/medicaldevices/safety/alertsandnotices/ucm615013.htm>). Of this reason, it is important to investigate this type of treatment in controlled, protocol-based studies, before general use is disseminated. Vaginal laser is a relatively new approach in the treatment of women with SUI. The treatment has shown promising results, and only the YAG laser has been evaluated in a randomized trial (Blaganje 2018).

Furthermore, many of the earlier studies have been supported by the private sector and so sceptics will claim that there is a potential of biased results (Conte C, Journal de l'Association française d'urologie et de la Societe française d'urologie. 2017). It is important that all new treatment-regimes in the public health care are tested and compared to existing regimes and placebo, not only medical drugs.

Transvaginal treatment with the MonaLisa Touch laser system has been shown to be safe and without major complications or side effects, when used in women with vaginal atrophy. The system is thought to work by stimulating growth and remodelling of collagens in the vaginal support tissue. Furthermore, it is assumed, that intravaginal laser treatment can stimulate the growth of urethral collagen, thereby reducing urethral mobility and increasing intraurethral pressure, and so should potentially reduce symptoms of SUI.

Our aim with this study is to determine if transvaginal CO₂ laser- treatment (DEKA SmartXide² Laser System, MonaLisa Touch), renders significant effect in women with SUI. To best test this hypothesis, the study will be performed in a prospective, randomised controlled fashion in our institution. We will measure the effect as patient reported improvement using a validated scale as well as an objective measurement.

Methods (3)

Study setting

Patient will be included from our hospital (a Danish academic hospital) among women referred with incontinence. Eligible patients will be randomized to either laser treatment or "sham" laser treatment.

Eligibility criteria (5)

The study will take place in the department of Gynecology and Obstetrics of Hvidovre University Hospital, Copenhagen Denmark in the period of May 2019 to May 2020. Inclusion criteria for the study cohort and controls will be patients i. referred from specialist gynecologists or GPs with SUI; ii. speak and understand Danish; iii. has a voiding diary that indicates stress incontinence; iv. older than 18 years of age; vii. with BMI under 35; viii. and present with mild to severe SUI evaluated after ICIQ-SF (slight (1-5), moderate (6-12), severe (13-18) and very severe (19-21), Kloving 2009). Exclusion criteria presence of pelvic organ prolapse greater than stage II by the POP-Q system, previous pelvic surgery, current infections, keloid formation, vaginal pain, dyspareunia and ongoing pregnancy.

Interventions

In this study, women will receive a series of three treatments using a fractional (pulsed) CO₂ laser system (SmartXide² MonaLisa Touch, DEKA M.E.L.A Srl, Florence, Italy), each performed in an outpatient setting without analgesia. A tubular laser-probe is inserted in the vaginal canal until reaching the vaginal vault. A burst of laser pulses is transmitted through the probe and deflected at 90° in four directions towards the vaginal wall, then rotated 45° for a second burst of pulses. Guided by markings on the probe, it is withdrawn

4mm and the procedure is repeated until reaching the introitus. Treatment parameters include power 30W, dwell time 1000 μ s, 1000 μ m spacing, using normal scan mode, with Smartstack setting for 1 at first application and 3 for the next two applications.

Both study- and placebo- treatments will be performed by specialist gynecologists employed in the department. Patients, who meet inclusion criteria and consent to study participation, will be randomized by computer service [REF] to conservative treatment, which encompass local estrogens (Vagifem 10 μ g twice weekly) if relevant (postmenopausal women) and pelvic floor training supervised by specialised physiotherapists in our own institution, whilst the study cohort will receive the same treatment with the addition of transvaginal laser applied thrice with 25- 45 days apart (CO₂ laser- treatment (DEKA SmartXide² Laser System, MonaLisa Touch). The controls will receive placebo treatment, with the use of the inactive laser, but relevant sound effects.

Outcomes

Primary outcome of the study is patient experienced improvement of SUI evaluated by standardized ICIQ-SF questionnaire.

Our secondary outcome is objective improvement as measured by standardized stress test performed by specialist nurse before treatment and 1-2 month after last laser or placebo treatment. The bladder is emptied with a catheter and 300ml of saline is inserted. The patient is then stood up wearing a pad with legs slightly apart and asked to forcefully cough 3 timers. The examiner registers whether there is incontinence as either yes or no as well as grams of urine leakage in the pad. Furthermore, side- effects both positive and negative as well as patient satisfaction will be registered by the use of patient questionnaires at 1-2 months post treatment.

Participant timeline

Timeline after inclusion

- 1st visit in outpatient clinic: evaluation by nurse or physician; instruction in minimal care treatment, pelvic examination, evaluation of bladder diary, evaluation of study eligibility and randomization. Baseline information registered in case report form and referral to physiotherapy.
- 2nd visit. 1st Laser/placebo treatment
- 3rd visit 2nd Laser/placebo treatment (between 20 and 40 days after previous treatment)
- 4th visit 3rd Laser/placebo treatment (between 20 and 40 days after previous treatment)
- 5th visit. Follow up 1-2 months after last treatment. ICIQ-SF questionnaires, clinical examination and standardized stress test. Information registered in case report form.

Both study-cohort and controls will receive pelvic floor training supervised by specialised physiotherapists. If the treatment is evaluated as unsuccessful, next treatment option will be considered.

4. Sample size

Based on variation and observed effect of more than 2 points from other studies (Blagajna 2018) on the ICIQ-UI SF scale we have calculated that 20 patients in each group would be sufficient even with 20% dropout to show a difference. The assumptions are significance level of 0,05 and a risk of type 2 error set to 20%.

Recruitment

All urogynecologist and specialised urogynecological nurses at the department will be actively involved in the study and will be actively including patients.

Methods: Assignment of interventions (for controlled trials)

Sequence generation

A computer will generate the numbers using blocks of 6.

Allocation concealment mechanism

Allocation will be hidden in a computer program.

Implementation

The data manager will do the sequence generation. Doctors at the urogynecological clinical will enroll patients and assignment will occur when patient data is submitted in the electronical case report form.

Blinding (masking)

The patient and the outcome assessor (nurse) will be blinded. However, the doctor performing the laser treatment cannot be blinded.

Unblinding will occur if a patient suffers adverse events that requires treatment or exclusion of the trial.

Methods: Data collection, management, and analysis

Data collection methods

Baseline data will be recorded: age, BMI, parity, ICIQ-UI SF, standardized stress test, degree of pelvic prolapse. All data will be saved in RedCAP, which will provide facilities for randomization as well as ensure that data are being stored according to Danish legislation.

ICIQ-UI SF is a validated scale for measuring degree of stress incontinence and has been used in many studies.

Data collection forms will be constructed in RedCap.

Both the study cohort and controls will be contacted by telephone, if they do not come for follow-up treatment or data-collection.

Nurses will be instructed in the standardized stress test.

Statistical methods

The post treatment scores will be compared using Students t-test for the primary outcome and chi square test for dichotomous outcomes. Our strategy is an intention to treat analysis when possible. Clinically significant differences of our primary outcome is probably at least 2 points.

Methods: Monitoring (6)

Data monitoring

All investigators will be part of the monitoring board and will decide whether the trial should be terminated. No interim analysis are planned due to the few patients involved.

Harms

All harms will be reported verbatim. Serious adverse events will be discussed by the monitoring board within two work days.

Auditing

No auditing is planned as the procedures and measurements will be carried out by very few health workers.

Ethics and dissemination

Research ethics approval

Relevant approvals from ethics committee and data protection agency will be obtained.

Protocol amendments

Protocol amendments will be reported to ethics committees and trial registries.

Consent or assent (12)

Written and oral consent will be obtained and documented recruiting gynaecologist or specialized nurse in the outpatient clinic. At the clinic patients are attended individually in a separate room. If they are interested they will be scheduled for treatment. In the mean time they can consult with their doctor or family.

Confidentiality

Data will be collected, stored and reported in accordance with Danish legislation and approval from the data protection agency will be obtained.

Declaration of interests

All investigators will have to provide a declaration of interest before the study begins. Investigators with conflicts to the manufacturer of the Laser device will not be able to participate in this study.

Access to data

Only investigators will have access to data. Data will either be anonymized or destroyed a few years after the study finishes.

Ancillary and post-trial care (11, 15)

As this treatment is already being used in Denmark, patients that suffer damage will be eligible to compensation through the 'Patienterstatningen'.

No participation fee for participant will be given.

Dissemination policy (13)

Results will be reported in peer reviews journals and the study results will be registered at clinicaltrials.gov.

Professional writes will not be used. We will share our data to the extent it does not interfere with privacy and Danish legislation.

Economy (10)

Hvidovre hospital has so far funded the project with 60.000. The project has been initiated by the authors of the protocol. Additional funding will be sought to employ a PhD student for managing data, doing analyses and writing the paper. The department will pay for salary of the nurses and treating physicians and the Laser is already at our institution.

Additional information to Danish ethics committee

7. Biological material

No biological material will be collected

8. Information from patient charts

We will ask patients permission to look up weight, height, medicine and prior illnesses from their chart. We will also ask permission to look up admission 12 months following last treatment. This is required to monitor adverse events.

9. Handling of patient information

All patient data will be safely stored in accordance with Danish legislation. Approval from the data protection agency will be obtained.

14. Research ethics

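### The stress-test outcome is defined as improvement, but the stated chi-square most naturally compares post-treatment results only; the recorded baseline test should be used

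*Protocol*

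**What the plan says.** The Outcomes section of the protocol sets the objective endpoint: "Our secondary outcome is objective improvement as measured by standardized stress test performed by specialist nurse before treatment and 1-2 month after last laser". The timing is the same for the sham arm. The result has two forms: "The examiner registers whether there is incontinence as either yes or no as well as grams of urine leakage in the pad".

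The test is also among the baseline variables under Data collection methods: "Baseline data will be recorded: age, BMI, parity, ICIQ-UI SF, standardized stress test, degree of pelvic prolapse".

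The analysis is one sentence under Statistical methods: "The post treatment scores will be compared using Students t-test for the primary outcome and chi square test for dichotomous outcomes". The section adds that the strategy is intention to treat where possible. It does not say what counts as improvement on the stress test, gives the baseline result no role, and names no comparison for grams.

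Under Eligibility criteria, a woman qualifies if she is referred with stress incontinence, "has a voiding diary that indicates stress incontinence", and she must "present with mild to severe SUI evaluated after ICIQ-SF". The severity bands listed there start at a score of 1. A positive stress test is not among the criteria.

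**The concern.** Improvement means change from a starting state. A table of post-treatment results by arm records a state, not a change. Because entry does not depend on the stress test, some women may not leak on it before treatment. A woman dry both times then falls in the same cell as one who leaked before and is dry afterwards.

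Two things follow. The between-arm difference is averaged over women who had nothing to gain on this test. And if one arm happens to receive more of them, that imbalance feeds directly into the comparison. The Introduction justifies the trial partly by the lack of controlled evidence and the suspicion of bias in earlier work, and it promises an objective measurement. The stress test is that measurement, so its sensitivity matters even though it is secondary.

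**Working it through.** **Inputs from the protocol.** 20 women per arm, allowing for 20% dropout, so 20 × 0.8 = 16 with a result; significance level 0.05 (taken as two-sided). The protocol states no power, effect size or dry rate for the stress test, so there is no figure of its own to reproduce here. The 20 per arm rests on the ICIQ-UI SF only.

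**Assumptions, none of them in the documents.** f = share dry at baseline, varied; s = share of those still dry at visit 5, 95-100% in both arms; dry rate at visit 5 among women who leaked at baseline, 60% (laser) vs 20% (sham).

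**Step 1: size of the observed difference.** The post-treatment dry rate in an arm is f·s + (1 - f)·p, where p is the dry rate among women who leaked at baseline. The term f·s is the same in both arms and cancels, so

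observed difference = (1 - f) × (p_laser - p_sham).

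With f = 0.30 and s = 1:
- sham: 0.30 + 0.70 × 0.20 = 0.44
- laser: 0.30 + 0.70 × 0.60 = 0.72
- difference: 0.28, against 0.40 among women who leaked at baseline

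At f = 10% and f = 50% the 40 points become 36 and 20.

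**Step 2: power of the plain chi-square, closed form.** For 44% vs 72% with 20 per arm, the mean rate is 0.58.
- Null SE = √(2 × 0.58 × 0.42 / 20) = 0.156
- Alternative SE = √((0.44 × 0.56 + 0.72 × 0.28) / 20) = 0.150
- z = (0.28 - 1.96 × 0.156) / 0.150 = -0.17, which gives power of about 43%

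**Step 3: simulation, 200,000 trials per scenario.** The plain uncorrected chi-square on all women is compared with a Mantel-Haenszel test stratified by the baseline result, without continuity correction. Ranges reflect s between 95% and 100%; a re-run agreed to within about one point.

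| Per arm | f | Plain chi-square | Stratified Mantel-Haenszel |
|---|---|---|---|
| 16 | 5% | 61% | 63% |
| 16 | 10% | 55-56% | 60-61% |
| 16 | 30% | 37% | 47-49% |
| 20 | 10% | 62% | 70-71% |
| 20 | 30% | 42% | 56-59% |

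The simulated 42% agrees with the 43% of step 2.

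**Step 4: imbalance.** With 20 per arm and f = 30%, the arms differ by three or more baseline-positive women in 39% of trials. The protocol plans blocks of 6 and names no stratification factor, so the design does not prevent this.

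**Step 5: checks on the remedy.**
- Type I error is about 4-6% for the plain test and about 5% or slightly below for the stratified test in nearly all scenarios.
- With a continuity correction, the Mantel-Haenszel test falls to 40-42% at 20 per arm and f = 30%, no better than the plain test.
- If only 80% of baseline-dry women stay dry, the gain at 16 per arm and f = 30% shrinks to 40% against 36%.
- Recoding the outcome as wet-to-dry in all women does not remove the dilution: baseline-dry women become fixed non-improvers and the difference is still multiplied by (1 - f).

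**The case against.** The strongest reply is that nothing is invalid here. Randomisation makes the post-treatment comparison a fair estimate of the effect in the women enrolled, and counting all of them fits the stated intention to treat. Calling the smaller difference dilution presumes that the effect in women who leaked at baseline is the right target, which is a choice of estimand. This stands: the point is one of efficiency and of fit with the stated outcome.

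Second, the protocol never names the dichotomous variable. The word scores fits the questionnaire best, so a chi-square on improved yes/no is not excluded, and a statistical analysis plan could define it. This stands in part. The reading is possible but not stated, no rule for improvement is given, and the wet-to-dry version carries the same factor (1 - f).

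Third, f is unknown. The test uses 300 ml, standing, with three forceful coughs, in women referred with stress incontinence and a supporting diary, so few may be dry. At 5-10% dry and 16 per arm the gain is only about 2-5 points. With a smaller effect (50% vs 30%), 10% dry and 16 per arm, it is 18% against 19%. Even with nobody dry at baseline, 16 per arm gives 67% for a 40-point effect, so the main limit is sample size, and no power is claimed for this outcome. All of this stands, and it sets the weight of the point.

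A reader might infer that women dry at baseline bias the result, that the protocol declares them successes, or that a large loss of power is established. The documents support none of these. Type I error holds, the protocol does not use that label, and a loss of 14-17 points (42% vs 56-59%) depends on an assumed f of 30%.

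**Conclusion.** The point holds as a mismatch between the stated outcome and the stated analysis, with a modest and uncertain cost in sensitivity. The outcome is improvement from a baseline test that is done and recorded, and the stated comparison most naturally ignores it. The dilution factor (1 - f) is exact if women dry at baseline fare alike in both arms; its value is unknown. Over the assumed range, using the baseline result adds about 2 points of power at f = 5% and 10-12 points at f = 30% with 16 per arm. These figures rest on dry rates of 60% vs 20% and on nearly all baseline-dry women staying dry. Neither the primary outcome nor the validity of the secondary comparison is affected. The change is worth making because it costs almost nothing and fixes the meaning of improvement before data are seen.

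**What to change.** In Statistical methods, state for the stress test:

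- Compare the visit-5 yes/no result between arms in all randomised women with a result, using a Mantel-Haenszel test without continuity correction, stratified by the baseline stress-test result.
- Report the matching Mantel-Haenszel risk difference with its confidence interval, so that test and estimate refer to the same women. This estimate still averages over women dry at baseline (about 28 points in the f = 30% example); what is gained is precision and protection against baseline imbalance.
- Report conversion from positive to negative among baseline-positive women as a supporting description only. It covers a different population from the test and should not serve as the main estimate.
- Compare visit-5 pad grams between arms, adjusted for baseline grams.

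Leave the entry criteria unchanged. The cost is a few lines of wording: both the yes/no result and the grams are registered at the test before treatment and again at follow-up, so no visit, procedure or additional woman is needed.

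### Side effects are asked about only once, 1-2 months after treatment; asking also at visits 3 and 4 would cheaply shorten recall for sessions 1 and 2

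*Protocol*

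**What the plan says.** Under Outcomes, after the primary and secondary outcomes, the protocol adds that "side- effects both positive and negative as well as patient satisfaction" will be "registered by the use of patient questionnaires at 1-2 months post treatment". The Participant timeline has one visit that fits this, visit 5: "Follow up 1-2 months after last treatment". Visits 2, 3 and 4 are listed only as the three laser or placebo sessions.

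The spacing of sessions is given twice. Participant timeline has "3rd visit 2nd Laser/placebo treatment (between 20 and 40 days after previous treatment", and the same range for the following session. Interventions has "transvaginal laser applied thrice with 25- 45 days apart".

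Other provisions touch on harms:
- Harms: harms are to be reported verbatim, and the monitoring board discusses serious events within two working days.
- Blinding (masking): a patient is unblinded for an event that needs treatment or exclusion.
- Section 8, Information from patient charts: admissions are looked up for 12 months after the last treatment.
- Data collection methods: "Both the study cohort and controls will be contacted by telephone, if they do not come for follow-up treatment or data-collection". The data forms do not yet exist: "Data collection forms will be constructed in RedCap".

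**The concern.** Part of the Introduction's case for the trial is that safety evidence for vaginal laser is thin. A sham-controlled record of mild effects is therefore something this trial can add. Sessions are given without analgesia, so brief discomfort after a session is a plausible effect, and it is the kind of effect that fades from memory over weeks to months.

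A single enquiry after all three sessions also has no stated means of separating effects by session. Interventions gives a different Smartstack setting for the first application than for the next two, so a record by session would be informative. (This implies no view on the settings.)

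The arms are small. With the planned 20 women per arm, one missed woman changes that arm's proportion by 1/20 = 5 percentage points. No analysis can recover an effect that was not asked about in time.

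**Working it through.** The protocol states no recall interval, so there is no figure of its own to reproduce. The check is calendar arithmetic for a woman who attends all three sessions.

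**Inputs**
- Interval between sessions, g: 20-40 days (Participant timeline) or 25-45 days (Interventions). Both are carried through because they disagree.
- Time from session 3 to the questionnaire, f: 1-2 months, taken as 30-61 days. The conversion to days is an assumption.

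**Formulas for time from session to questionnaire**
- Session 1: 2g + f
- Session 2: g + f
- Session 3: f

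**Results as the protocol stands**

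| Session | g = 20-40 days | g = 25-45 days |
|---|---|---|
| 1 | 2×20+30 = 70 to 2×40+61 = 141 | 2×25+30 = 80 to 2×45+61 = 151 |
| 2 | 20+30 = 50 to 40+61 = 101 | 25+30 = 55 to 45+61 = 106 |
| 3 | 30 to 61 | 30 to 61 |

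Sensitivity to the month length: with 28-62 days, session 1 is 68-142 or 78-152 days. With 30-60 days it is 70-140 or 80-150 days. The limits move by at most 2 days.

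**Results if women are also asked at visits 3 and 4**
- Session 1, asked about at visit 3: recall is g, that is 20-40 or 25-45 days. The saving is g + f = 50-101 or 55-106 days.
- Session 2, asked about at visit 4: recall is g, 20-40 or 25-45 days. The saving is f = 30-61 days.
- Session 3, asked about at visit 5: unchanged at 30-61 days.
- The longest recall for any session falls from 141 or 151 days to 61 days.

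**Does another provision already ask?** Verbatim reporting says how harms are reported, with no schedule or prompt. Board discussion covers serious events. Unblinding covers events needing treatment or exclusion. The chart look-up finds admissions. The telephone call reaches women who miss an appointment. None of these asks an attending woman about mild effects between sessions.

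**The case against.** The strongest reply is that one enquiry at follow-up contradicts nothing in the protocol, and that the trial's aim is efficacy. That is right: this is a better collection schedule, not the correction of an error. Four further points limit the concern, and each stands at least in part.

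- **The timeline is a sketch.** It does not name the side-effect questionnaire at visit 5 or the baseline stress test at visit 1, although both are required elsewhere. Women meet a gynecologist at visits 2 to 4 and may volunteer complaints, and the forms still to be built might include a field. A reader might infer that nobody will ask at these visits. The protocol supports only the weaker statement that no enquiry is scheduled.
- **The longest recall belongs to session 1 alone.** An effect that recurs at session 3 can still be reported after 30-61 days. For a count of women ever affected, loss requires an effect of session 1 or 2 that does not recur and is forgotten.
- **The remedy is partial.** Asking 20-45 days after a session is still weeks later, and session 3 gains nothing. The largest saving falls on the first session, the one given at a different Smartstack setting.
- **Asking more often has a price.** In a sham-controlled trial with a patient-reported primary outcome, questions about side effects before sessions 2 and 3 could lead some women to guess their allocation.

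Two stronger readings should be resisted. A reader might infer a biased comparison of side effects between arms, but both arms have the same schedule and the protocol gives no sign of unequal recall. A reader might also infer that no safety record exists for vaginal laser in stress incontinence. The Introduction does report YAG-laser studies that included such women and found no serious complications or side effects; it is its safety statement for the MonaLisa Touch system that concerns women with vaginal atrophy.

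**Conclusion.** The point holds as a cheap improvement. The only scheduled side-effect enquiry comes 70-141 or 80-151 days after session 1, 50-101 or 55-106 days after session 2, and 30-61 days after session 3. What may be lost is confined to mild, short-lived effects of sessions 1 or 2 that do not recur at session 3, need no treatment and are not volunteered. The main risk is under-counting in both arms, and the protocol does not allow its size to be estimated. The primary analysis and the sample size are unaffected.

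This rests on reading 1-2 months as 30-61 days, on attendance at all three sessions, and on visit 5 being the time of the questionnaire, since no other visit fits.

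**What to change.** Use one short, neutrally worded side-effect form, identical in both arms:

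- **Visits 3 and 4:** each woman completes it herself before the session, about the previous session. Self-completion matters because the doctor giving the treatment knows the allocation.
- **Visit 5:** she completes it after the ICIQ-SF, so that it cannot colour the primary outcome at that visit. It is kept from the blinded nurse who does the stress test.

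The timing of visit 5 should stay as it is for this purpose, because the ICIQ-SF is collected at the same visit and would move with it.

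The cost is one form at two visits that already exist, and a few minutes of each woman's time. The risk of allocation guesses before the primary outcome is limited by identical neutral wording but not removed. Recall of 20-40 or 25-45 days remains for sessions 1 and 2.

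Separately, the two session intervals, 25-45 days under Interventions and 20-40 days in the Participant timeline, contradict each other and must be reconciled.
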